### Revision History

[figure not shown]
Document number	Date	Comments
EX-MKTG-101	February 28, 2019	First draft (v 1.0)
EX-MKTG-101	March 4, 2019	FINAL

Confidential

1

# 1 Introduction

---

According to a 2018 international contact lens prescribing report, silicone hydrogel materials accounted for 76% of soft lenses prescribed and for more than 90% of fits in some markets. In the US for 2018, silicone hydrogel lenses have a reported usage at 69% of fits. Data from Contact Lens Spectrum’s market research in the US showed that, across all contact lens designs, most of the reported fits and refits are with soft spherical contact lenses (49% versus 48% in 2017). CooperVision’s Avaira Vitality™ sphere lenses use a third generation silicone hydrogel material which makes the lens inherently wettable with no surface treatments, and uses naturally wettable building blocks to improve compatibility between silicone and hydrophilic domains. This, combined with the higher water content of Avaira Vitality™ ensures a high performing, comfortable lens.

Clariti Elite sphere lenses are part of a generation of silicone hydrogel portfolio from CooperVision which will be discontinued from the market in the near future. Therefore, CooperVision is interested in evaluating the clinical performance of existing wearers of Clariti Elite sphere lenses after a refit with Avaira Vitality™ silicone hydrogel sphere lenses over 4-weeks of daily wear.

## 2 Study Objective

---

The aim of this prospective study is to evaluate the clinical performance of habitual wearers of Clariti Elite sphere lenses after a refit with Avaira Vitality sphere lenses for 4 weeks of daily wear.

**The primary variables of interest are:**

- Lens fitting characteristics

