### 3.1 Study Hypothesis

---

- Null hypothesis ( $H_0$ ): There is no difference in lens performance between the study lenses for the key variables tested.
- Alternative hypothesis ( $H_1$ ): There is a difference in lens performance between the study lenses for the key variables tested.

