### 8.2.6 Masking and Control of Study Materials

The study contact lenses will be **masked to the subject only**. Study lenses will be transferred, by an assistant, out of their packaging to unmarked new contact lens cases filled with unpreserved sterile saline just prior to dispensing to maintain subject masking of the study lenses.

- [REDACTED]
  - [REDACTED]
    - [REDACTED]
    - [REDACTED]
  - [REDACTED]
    - [REDACTED]
    - [REDACTED]
- Lens Fit
  - Lens centration (centered/slightly decentered/substantially decentered)
  - Corneal coverage [Y/N]
  - Post-blink movement (0 - 5 Likert scale)
  - Lens tightness. Push up test (0% to 100%, 50% optimum)
  - Overall fit acceptance (0 - 4) and reason if Grade 2 or less.
  - Remove study lenses and perform slit lamp examination
- [REDACTED]
  - [REDACTED]
    - [REDACTED]
    - [REDACTED]
    - [REDACTED]
    - [REDACTED]
    - [REDACTED]
  - [REDACTED]
    - [REDACTED]
    - [REDACTED]
    - [REDACTED]
    - [REDACTED]

Visit 3b: Dispense Avaira Vitality Lenses

The study subjects will undergo a trial fit in each eye with the second pair of study lenses.

- The performance of the second pair of study lenses should be assessed after 10 - 15 minutes settling time. The same variables as those collected on *visit 2, section 8.3.2* will be assessed.

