### 10.2 Sample size

A sample size was calculated using data from a previous study. Assuming a standard deviation of 1.9 points, with 84% power and an alpha level of 0.05, a sample size of 34 subjects is required to detect a difference of 1.0 points, (0-10 scale), between lenses [REDACTED] 40 subjects will be enrolled to account for potential drops outs or discontinuations.

Figure 1. Sample size calculation (Minitab 16 Statistics software)

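### The primary variable covers five separately scored lens-fit items with no designated item, time point or multiplicity rule; if each is tested at 0.05 and any one counts, the false-positive rate is up to 22.6%

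*Combined protocol and SAP*

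**What the plan says.** Section 2 uses the plural, "The primary variables of interest are", and shows a single entry below it: "Lens fitting characteristics". Section 4 likewise presents the study as a comparison of the two lenses' fitting characteristics.

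The content of that entry appears only in the visit procedures. The Lens Fit list for Visit 3a (section 8.3.3) has five scored items:

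- centration, in three categories;
- corneal coverage, yes or no;
- post-blink movement, 0 to 5;
- push-up tightness, 0 to 100% with 50% as optimum;
- the last, "Overall fit acceptance (0 - 4) and reason if Grade 2 or less".

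Sections 8.3.4 and 8.3.5 repeat the Visit 3a assessments for Avaira Vitality after 2 and after 4 weeks.

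The alternative hypothesis in section 3.1 is: "There is a difference in lens performance between the study lenses for the key variables tested". It does not say whether one variable or all of them must differ.

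Section 10.1 assigns paired t-tests or analysis of variance, the Wilcoxon signed-rank test, or chi-square according to data type. It carries no redaction marks, and it gives no significance level, primary item, composite, order of testing or multiplicity adjustment. Section 10.2 contains the only level in the documents, "an alpha level of 0.05", for a 1.0-point difference on a 0-10 scale. The words after that difference, where the variable might be named, are blacked out.

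**The concern.** The five items are on different scales and no composite is defined, so section 10.1 can only be applied item by item. That yields five unranked primary comparisons. The null in section 3.1 asserts no difference on the key variables, and a difference on any one of them contradicts it. Nothing visible requires agreement between items or says which one decides.

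The risk is that a single nominally significant item is reported as a primary difference between the lenses, and that the item is picked after the data are seen. The chance of at least one such result when the lenses fit alike exceeds the level a reader would attach to one primary test.

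**Working it through.** **Inputs from the documents.** Five fit items (section 8.3.3, Visit 3a); alpha 0.05, 84% power, SD 1.9, difference 1.0 and n = 34 (section 10.2).

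**Assumptions not in the documents.** Each item is tested two-sided at 0.05; any one significant item counts as a primary difference; the correlation between items is between 0 and 0.9.

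**1. The plan's own figure.** For a paired t-test, the noncentrality is (1.0/1.9) × √34 = 0.526 × 5.831 = 3.07 on 33 degrees of freedom. Two-sided power at 0.05 is 84.6%. With n = 33 it is 83.4%, so 34 is the smallest n that reaches 84%, and the plan's figure is reproduced. A one-sided test would give 91.3%, so the 0.05 in section 10.2 is two-sided. The calculation covers one test.

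**2. Five independent tests.** 1 − 0.95⁵ = 1 − 0.774 = 22.6%.

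**3. Five correlated tests.** Simulation of five equicorrelated paired t-tests, n = 34, 60,000 runs per setting:

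| Assumed correlation | At least one false positive |
|---|---|
| 0.3 | 20.9% |
| 0.5 | 18.5% |
| 0.7 | 15.1% |
| 0.8 | 13.0% |
| 0.9 | 10.3% |

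The simulation treats the items as continuous and normal. Coarse, tied scales may behave differently.

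**4. Coverage near ceiling.** If the two lenses disagree on coverage in 5% of subjects, an exact McNemar test on 34 pairs rejects falsely less than 0.1% of the time. Coverage then contributes almost nothing, and four tests remain: 1 − 0.95⁴ = 18.5% if independent, 13.3% at correlation 0.7. Section 10.1 names chi-square rather than McNemar. An ordinary chi-square, with 34 results per lens treated as independent, has size 0.5% at a 2% failure rate and 3.5% at a 5% failure rate. The size of the reduction therefore depends on the test and on the failure rate.

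**5. Effect of adjustment.** At 0.05/5 = 0.01 per test, five independent tests give 1 − 0.99⁵ = 4.9%. Holm starts at the same 0.01 for five items, or at 0.05/4 = 0.0125 for four.

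**6. Price in power, as illustration only.** With the 0-10 scale inputs of section 10.2, power at 0.01 with n = 34 is 63.2%, and 50 completers would be needed for 84%. No fit item is on that scale, so these figures do not transfer to any of them.

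**The case against.** The strongest reply is that much of the inflation rests on rules the protocol never states.

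- **Level.** A reader might infer that each fit item is tested at 0.05 and that the plan promises a 5% error rate for its primary outcome. It says neither. Section 10.1 gives no level, and the 0.05 in section 10.2 belongs to a 0-10 scale outcome whose name is not visible. This objection stands. Using 0.05 for the fit items is a reasonable default because no other level is given, but it is an assumption.
- **Decision rule.** If all five items had to differ, the error would be at most 5%. Section 3.1 does not settle this. The any-one reading fits the wording of the null better, and no all-items rule is stated, but the inflation is conditional on that reading.
- **Number of tests.** A reader might add the week-2 visit and quote 1 − 0.95¹⁰ = 40.1% for ten tests. The documents do not support this. Week 2 is scheduled only for Avaira Vitality, so it has no Clariti Elite counterpart; the objective refers to 4 weeks of wear; and independence is implausible for the same items repeated in the same subjects.
- **Purpose.** The study evaluates a refit from a lens that is to be discontinued, and no superiority claim is visible. A spurious difference may not be the costliest error here, and stricter thresholds make a real difference easier to miss. This limits how serious the point is. It does not explain why the primary item and visit are left open while a hypothesis of difference is tested.

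**Conclusion.** The point holds as a gap in specification with a conditional size. The visible text leaves five fit items unranked under one primary entry, with no deciding visit and no multiplicity rule. If each is tested two-sided at 0.05 and any one counts, the family-wise false-positive rate is 22.6% for independent items and falls to about 10% at a correlation of 0.9. It is lower again if coverage hardly varies. Across the five-item correlations examined it stays at about twice 5% or more. The documents do not support saying that the plan breaches a stated 5% rate, because it states none for the primary family. The change is worth making and inexpensive. The study could still run and report its fit data descriptively without it.

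**What to change.** In sections 2 and 10.1, adopt one of two forms, and state the two-sided level and what counts as a primary difference.

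- **One primary item.** Name one fit item, compared at 4 weeks of wear on each lens (Visit 3a against Visit 5), tested at 0.05. Overall fit acceptance (0 to 4) is one reasonable choice, but nothing in the documents requires it over movement or tightness. Make the other four items secondary, either with Holm adjustment across the four or labelled descriptive.
- **Five primary items.** Keep all five at the same visit pair, with Holm adjustment across the five.

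**Cost.** No added visits or measurements. The first Holm step is stricter: 0.0125 for four secondary items, 0.01 for five primary items, with some loss of power for real differences. More than wording is involved: section 10.2 must be rechecked or restated for the chosen item or items. Its SD of 1.9 and difference of 1.0 refer to a 0-10 scale that no fit item uses, and the documents give no SD for any of the five.

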**The secondary variables of interest are:**

- Wearing times (average and comfortable)

[REDACTED]

- [REDACTED]
- [REDACTED]
- [REDACTED]
- [REDACTED]
- [REDACTED]
- [REDACTED]

## 3 Study Hypothesis

---

### 3.1 Study Hypothesis

---

- Null hypothesis ( $H_0$ ): There is no difference in lens performance between the study lenses for the key variables tested.
- Alternative hypothesis ( $H_1$ ): There is a difference in lens performance between the study lenses for the key variables tested.

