## 4 Study Design

---

This is a prospective, subject masked; bilateral, 4-week refit study comparing the fitting characteristics of Clariti Elite sphere lenses, (somofilcon A), against Avaira Vitality silicone hydrogel sphere lenses (fanfilcon A). A total of 40 subjects will be enrolled with the aim of completing 34.

Subject's will be evaluated at the first visit and then fitted with both study lenses to confirm lens fit and optimize visual acuity if needed. At the second visit, the first pair of study lenses, (e.g. somofilcon A), will be dispensed and worn for 4-weeks. After 4-weeks of daily wear with the first pair, subjects will return for a third evaluation and then fitted with the second pair, (e.g. fanfilcon A), of study lenses for 4-weeks. A fourth visit will be scheduled after 2-weeks of lens wear. A fifth and final visit will be scheduled after 4-week of lens wear. The study timeline is shown in Appendix 2.

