### **8.1 Participants**

---

Approximately 40 habitual soft contact lens wearers will be enrolled. Each subject will be required to attend up to five scheduled study visits over a period of approximately two months.

Each subject will be given a unique ID number. Additionally, all subjects must meet the study inclusion and exclusion criteria listed below.

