#### **8.1.1 Inclusion criteria**

A person is eligible for inclusion in the study if he/she:

- Is between 18 and 40 years of age (inclusive)
- Has had a self-reported visual exam in the last two years
- Is an adapted soft contact lens wearer

- Has a contact lens spherical prescription between – 0.25 to – 8.00 (inclusive)
- Have no less than -0.75D of astigmatism in both eyes.
- Can achieve best corrected spectacle distance visual acuity of 20/25 (0.10 logMAR) or better in each eye.
- Can achieve a distance visual acuity of 20/30 (0.18 logMAR) or better in each eye with the study contact lenses.
- Has clear corneas and no active ocular disease
- Has read, understood and signed the information consent letter.
- Patient contact lens refraction should fit within the available parameters of the study lenses.
- Is willing to comply with the wear schedule (at least 5 days per week, > 8 hours/day assuming there are no contraindications for doing so).
- Is willing to comply with the visit schedule

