### 10.1 Statistical analysis

Summary statistics will be produced (e.g. mean, standard deviation). Differences between lenses will be compared using Paired t-tests. Paired t-tests / analysis of variance for normal (interval/continuous) data, Wilcoxon's signed ranks test for non-normal (ordinal) data, chi-squares test for nominal data. A binomial test will be used to evaluate lens preference questions. All participants who are evaluated will be used in the analysis. In the event of missing data, individual data points will be excluded in the analysis and not extrapolated from the collected data.

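### The objective is about habitual Clariti Elite wearers, but eligibility admits any adapted soft lens wearer; secondarily, what reads as a single-order refit is worded as a between-lens difference

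*Combined protocol and SAP*

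**What the plan says.** **Population.** Section 1 explains that Clariti Elite is to be discontinued and that the sponsor is interested in "evaluating the clinical performance of existing wearers of Clariti Elite sphere lenses after a refit with" Avaira Vitality. Section 2 sets the aim as "to evaluate the clinical performance of habitual wearers of Clariti Elite sphere lenses after a refit with Avaira Vitality sphere lenses". The Visit 5 text (8.3.5) adds a preference question that treats Clariti Elite as the habitual lens and Avaira Vitality as the test lens. Section 8.1, however, says "Approximately 40 habitual soft contact lens wearers will be enrolled", and the only inclusion criterion on previous lens wear (8.1.1) is "Is an adapted soft contact lens wearer". The exclusion list (8.1.2) names no brand.

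**Framing.** The alternative hypothesis (3.1) is "There is a difference in lens performance between the study lenses for the key variables tested". Section 4 describes a refit study "comparing the fitting characteristics of Clariti Elite sphere lenses, (somofilcon A), against Avaira Vitality silicone hydrogel sphere lenses (fanfilcon A"). Section 10.1 says "Differences between lenses will be compared using Paired t-tests" and "A binomial test will be used to evaluate lens preference questions". The visit titles in the contents list and section 8.3 dispense Clariti Elite at Visit 2 and Avaira Vitality at Visit 3, with Avaira follow-up at Visits 4 and 5. Section 4 names the lens in each position only as an example (e.g.). Section 8.2.6 masks the lenses to the subject alone. The primary variable (section 2) is lens fitting characteristics; the fit list before Visit 3b has centration, coverage, movement, push-up and overall acceptance recorded at the visit.

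**The concern.** The reason for the study is that existing Clariti Elite wearers will have to move to another lens. If the sample includes people who habitually wear something else, Clariti Elite is itself a refit for them. Their Avaira result then describes a second change of lens within the study, not a move away from a long-worn lens. A pooled result may not describe the group the sponsor wants to know about, and the preference question would carry a false label for part of the sample.

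The framing matters for what may be concluded. If everyone wears Clariti first and Avaira second, a significant paired test would be reported as support for a difference between lenses. The data would show a change from the first wearing period to the second, in which lens, period and the expectation of an unmasked grader are mixed. Preference is asked at the end of the Avaira period, so recency is mixed in as well.

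**Working it through.** **1. The plan's own sample size.** Inputs from 10.2: SD 1.9, difference 1.0, alpha 0.05, power 84%, n = 34. I take 1.9 as the SD of paired differences and the test as two-sided, in line with 3.1. Noncentrality = (1.0/1.9) × √34 = 3.07; the critical t on 33 df is 2.03; power = 0.846. At n = 33 power is 0.834, so 34 is the smallest n that reaches 84%. Enrolling 40 allows for 6/40 = 15% loss. The figure reproduces and is not at issue.

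**2. Population, side by side.**
- Sections 1, 2 and 8.3.5: existing or habitual Clariti Elite wearers.
- Sections 8.1 and 8.1.1: habitual or adapted soft lens wearers, with no brand named.
- Section 8.1.2: no brand restriction added.

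A subject who has never worn Clariti Elite can satisfy every listed criterion. The two descriptions differ, and nothing readable joins them.

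**3. Size of the population point.** The documents give no share of Clariti wearers, so I assume 100%, 50% and 25% of 34 completers: 34, 17 and 8.5 (about 9). To show what each number supports, take an observed preference of 50%. The Wilson 95% half-width at 50% is z / (2√(n + z²)), with z = 1.96:
- n = 34: 1.96 / (2√37.84) = 0.159, interval 34% to 66%.
- n = 17: 1.96 / (2√20.84) = 0.215, interval 29% to 71%.
- n = 9: 1.96 / (2√12.84) = 0.273, interval 23% to 77%.

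Preference is not the primary variable; it is used here only because a proportion makes the loss of precision easy to see.

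**4. Order and masking.** The visit titles give one sequence. No readable section describes randomisation or counterbalancing, the contents list has no such heading, and 10.1 has no period or order term. With one sequence, mean(second period − first period) = lens effect + period effect + grading effect, and nothing in the design estimates these separately.

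**5. Illustrations of that mixing. Every bias size here is assumed.**
- Paired t-test, n = 34, SD 1.9, no true lens difference: a period effect of 0, 0.25, 0.5 or 1.0 points gives rejection rates of 0.05, 0.116, 0.319 or 0.846. The measure behind the 0–10 scale is redacted.
- Overall fit acceptance (0–4), n = 34, one value per subject, one-grade changes only, so that the Wilcoxon test reduces to z = (up − down)/√(up + down). At 15% up and 15% down it rejects 4%. At 25%/10% (net 0.15 × 34 = 5.1 subjects) it rejects 30%, and at 30%/10% (net 6.8) 45%. An exact version gives 2%, 22% and 36%.
- Preference, all 34 answering, null taken as 50:50 (10.1 states none): the two-sided exact test needs 24 of 34. It rejects 2.4% if preference is truly 50:50, and 14% or 31% if 60% or 65% favour the lens worn last.

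**6. Effect on N.** Restating the aim as change after refit leaves step 1 unchanged. If the order were in fact balanced (17/17, period-adjusted, 32 df, same SD, no carryover), power at 34 would be 0.845, so N would not move either.

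**The case against.** The strongest reply is that a single-order refit is a legitimate design. The plan calls itself a refit study, states a refit objective and openly limits masking to the subject. Differences between lenses is ordinary shorthand for a paired contrast, and the readable text makes no superiority claim. That stands, and is why the framing is a matter of interpretation, not a design error.

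The order is also a reading, not a certainty. Section 4 says e.g. for both pairs, and sections 8.2.7 to 8.3.2 and the Appendix 2 timeline cannot be read. The visit titles strongly favour one order, but wording that asserts a fixed order must wait until section 4 is reconciled with them. An eligibility check in the unreadable Visit 1 text is likewise possible, although it would not remove the mismatch with 8.1.1.

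On population, every subject wears Clariti Elite for four weeks in the study, if the order is as the titles say. A reader might infer from step 3 that only 17 or 9 subjects would be useful. The documents do not support that: all completers inform a change from Clariti to Avaira, and the smaller counts apply only to the strict habitual group.

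A reader might also infer from step 5 that the false-positive rate is 30% or more. That is not supported either. No bias size comes from the documents, and the figures show sensitivity only.

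**Conclusion.** The population mismatch is wrong as written and should be corrected. Sections 1, 2 and 8.3.5 name one population, and 8.1 and 8.1.1 admit a wider one. Its size depends on a share the documents do not give; under the assumed range, between 34 and about 9 completers would represent the population in the objective. Four weeks of Clariti wear in the study softens the mismatch but does not make someone a habitual wearer.

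The framing point holds as a limit on interpretation, with medium confidence because the order is not fully readable. On the visit titles, with masking of the subject only and fit graded at the visit, the hypothesis and tests cannot attribute a difference to the lens. The documents do not support going further and calling the design invalid, the sample size wrong or the results biased by a known amount.

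**What to change.** **Population: reconcile 8.1 and 8.1.1 with sections 1, 2 and 8.3.5. The sponsor chooses the direction.**
- Either 8.1 and 8.1.1 name habitual Clariti Elite wear. Cost: possibly slower recruitment at the single site.
- Or sections 1 and 2 are widened to soft lens wearers, and the Visit 5 label changes, for example to first study lens in place of habitual. Record the habitual lens at Visit 1 if this is not already done, and report habitual Clariti wearers separately. Cost: one baseline item, subgroup reporting and some distance from the discontinuation question.

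**Framing: first reconcile the two e.g. phrases in section 4 with the visit titles.** If the order is fixed:
- Reword 3.1, 4 and 10.1 as within-subject change after refit from Clariti Elite to Avaira Vitality. The sponsor should name the analysis visit, since Visits 4 and 5 collect the same variables. Use paired methods suited to each item's scale; a subtraction does not suit yes/no coverage or three-category centration.
- State with the conclusions that order was fixed, that fit grading was not masked and that change cannot be attributed to the lens alone.
- Report preference as a proportion with a 95% CI, and do not read the binomial test as a lens effect.

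If the order is not fixed, say how it is allocated and bring the visit titles and 10.1 into line.

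Visits, lenses and N = 34 are unchanged. The main cost of the fixed-order wording is a weaker permitted conclusion.
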